4.4 Safety

Safety parameters will be evaluated for the safety analysis data set.

4.4.1 Adverse Events

The treatment emergent adverse events will be tabulated in the following categories:

- Cutaneous
 - Outside of treatment area
 - Leo 43204 Gel 0.018%
 - Vehicle
- Non-cutaneous

The split between cutaneous and non-cutaneous will be based on the MedDRA preferred term text as follows:

- Cutaneous
 - Application site plain
 - Application site pruritus
- Non-cutaneous

- Headache
- Nausea

Frequencies, incidences and incidence rates for treatment emergent adverse events will be presented in the following tables

- Overall summary table of adverse events
- Adverse events presented by system organ class and preferred term
- Adverse events presented by system organ class and preferred term and severity
- Related adverse events presented by system organ class and preferred term

All adverse events will be listed split by treatment emergent and non-treatment emergent. Adverse events leading to withdrawal or discontinuation of treatment will be listed.

A listing of unacceptable LSR events, following section 11.3.10 in the protocol, and LSR scores for not administering the 2nd or 3rd treatment (table 1 in protocol) will be shown together with reason for no treatment.

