5.2 Secondary Endpoints

- Inflammatory lesion count in the treatment area for LEO 43204 gel and vehicle gel at Week 12.
- Non-inflammatory lesion count in the treatment area for LEO 43204 gel and vehicle gel at Week 12.
- Investigator's Global Assessment of the treatment area for LEO 43204 gel and vehicle gel at Week 12.
- Composite and component LSR score at all visits
- Occurrence of unacceptable LSR scores or unacceptable safety and tolerability events at all visits (as described in section 12)

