11.3.10 Interim Analysis

After Week 2 (Visit 7) for specified number of subjects (refer to section 6.1) along the course of the trial analyses of blinded data will be performed evaluating the safety profile and the LSRs (refer to section 12).

The analyses will include:

- List of adverse event, using investigators term
- Number of subjects with:

One of the following scores on the LSR scale at any time:

- Grade 4 crusting
- Grade 4 erosion / ulceration
- Grade 4 vesiculation / pustulation extending significantly outside the treatment area

Or two or more of the following scores on the LSR scale at any time:

- Grade 4 erythema
 - Grade 3 crusting
 - Grade 4 swelling extending significantly outside the treatment area
 - Grade 3 erosion / ulceration
 - Grade 3 vesiculation / pustulation
- Descriptive statistics of composite and components of LSRs by visit and lateral side
 - Plots of mean and individual profiles of composite LSRs by visit and lateral side
 - Descriptive statistics of maximum of right and left side composite and component LSRs by visit

- Plots of mean and individual profiles of maximum of right and left side composite LSRs by visit
- List of individual component LSRs

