Non-inflammatory lesions	477345	657616	100

12 Trial Committees

The Safety Review Committee will comprise the following members:

- The International Coordinating Investigator
- Sponsor's medical expert
- Sponsor's Head of Translational Medicine
- Sponsor's pharmacovigilance expert
- Sponsor's Statistician
- The ICTM

Primary functions of the Committee:

- Operate to written procedures defined by the Safety Review Committee Charter for the trial.
- Document decision in the meeting minutes.

- Convene to review safety and tolerability after the last subject in cohort 1, 2 and 3 has completed the Week 2 follow-up visit (Visit 7).
- Decide whether quality of data is sufficient and whether unacceptable LSRs, safety or tolerability events have occurred necessitating termination of the clinical trial.

Prior to dosing of the first subject, the Safety Review Committee Charter will be finalised detailing the evaluation procedure and processes for immediate communication between sites.

Unacceptable LSR scores, safety and tolerability events:

Unacceptable safety and tolerability events in an individual subject are defined as 1) clinically relevant signs or symptoms observed, which in the opinion of the investigator are deemed unacceptable or 2) one or more of the following LSRs:

- Grade 4 crusting
- Grade 4 erosion / ulceration
- Grade 4 vesiculation / pustulation extending significantly outside the treatment area

Or two or more of the following:

- Grade 4 erythema
- Grade 3 crusting
- Grade 4 swelling extending significantly outside the treatment area
- Grade 3 erosion / ulceration
- Grade 3 vesiculation / pustulation

Criteria for terminating the trial:

The trial will be terminated if the perception of the benefit/risk ratio (judged from clinical symptoms, signs and/or (S)AEs) becomes unfavorable for the continuation of the trial.

- Any decision regarding premature termination of the entire trial will be made after mutual agreement between the Investigator and the sponsor.
- The sponsor reserves the right to cancel the trial at any time
- Due to the design of the trial, there are no statistical criteria for trial termination.
- The cumulative frequencies of subjects with unacceptable LSRs, safety and tolerability events (as defined above) that will strongly support the decision for trial termination are:

- 2 out of 3 subjects with unacceptable LSRs, safety and tolerability events after Cohort 1

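### The SAP 4.4.1 listing applies only the LSR-grade limb of the section 12 unacceptable-event definition, and no available output summarises the full secondary endpoint of Protocol 5.2

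*SAP*

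**What the plan says.** The last secondary endpoint in Protocol 5.2 is "Occurrence of unacceptable LSR scores or unacceptable safety and tolerability events at all visits (as described in section 12".

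Protocol section 12 defines an unacceptable event in an individual subject by either of two limbs. Limb 1 is "clinically relevant signs or symptoms observed, which in the opinion of the investigator are deemed unacceptable". Limb 2 is a list of LSR grades: any one of three scores, or two or more of five others. The same section gives frequencies that would strongly support stopping the trial (2 of 3, 3 of 9 and 5 of 15 subjects). It ties them to the same definition: "The cumulative frequencies of subjects with unacceptable LSRs, safety and tolerability events (as defined above".

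Protocol 11.3.10 is the blinded interim analysis. It refers to section 12 in general terms, but the subject count it specifies has two parts: "One of the following scores on the LSR scale at any time" and "Or two or more of the following scores on the LSR scale at any time". Both are LSR grades. Its adverse event output is a plain list.

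SAP 4.4.1 plans "A listing of unacceptable LSR events, following section 11.3.10 in the protocol", shown with the Table 1 scores for withholding a second or third application and the reason for no treatment.

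**The concern.** The endpoint and the section 12 frequencies rest on a definition with two limbs. The one planned count, and the one planned final listing of these events, use a rule with a single limb. A subject with a reaction that the investigator judged unacceptable, but whose LSR grades stayed below the list, meets the endpoint and is neither counted in 11.3.10 nor identified as an event in the SAP listing.

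Safety and tolerability is the trial's secondary objective, and Protocol 3.3.1 says it is unknown whether subjects with acne will have a different safety profile from the actinic keratosis population. If the LSR listing is the only place where unacceptable events are drawn together, the clinical trial report could present a narrower event as if it were the 5.2 endpoint.

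**Working it through.** The documents give no figure to reproduce. The check sets the definitions and outputs side by side.

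**1. Compare the rules.**

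| Place | Investigator judgement (limb 1) | LSR grades (limb 2) | Timing stated |
|---|---|---|---|
| Protocol 5.2, by reference to section 12 | yes | yes | all visits |
| Protocol section 12 | yes | yes (3 single scores; two or more of 5) | none for combining scores |
| Protocol 11.3.10 count | no | yes, same 3 and same 5 | any time |
| SAP 4.4.1 listing | no | yes, by reference to 11.3.10 | as 11.3.10 |

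The LSR grades in 11.3.10 match limb 2 item for item. Limb 1 is absent.

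**2. Look for a final summary elsewhere.**

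- Protocol 11.3.5 covers lesion counts and IGA.
- Protocol 11.3.8 covers adverse events, including a list of those leading to withdrawal or discontinuation.
- Protocol 11.3.9.1 covers LSR grades, the composite score and a table of LSRs that led to withdrawal.
- SAP 4.3.2 covers efficacy and questionnaires, and SAP 4.4.2 covers vital signs.
- The three figures in SAP 6 show lesion counts and composite LSRs.

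None gives the number of subjects meeting the section 12 definition. The only planned count is the interim one, at committee reviews after Cohorts 1 to 3, which hold 3 + 6 + 6 = 15 of the 40 planned subjects.

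**3. Look for traces of limb 1.** Protocol 6.1 has the reason for not treating recorded, and the second of its three criteria is the investigator's judgement. Withdrawal under Protocol 7.7 can be for events the investigator or the subject finds unacceptable, so it mixes two judgements. The action codes in 9.2.1 record what was done with the medication, not whether the event was judged unacceptable. After Day 3 there is no application left to withhold, so withdrawal is the main remaining source, although the endpoint runs to Week 12. None of these outputs labels or counts the judgement, or joins it to limb 2.

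**4. Direction of the difference.** Let O be the number of subjects counted by 11.3.10 and S the number meeting section 12. Let a be the subjects who meet limb 1 and are not in O. Let b be the subjects who are in O only because two scores from the five-score list occurred at different times, and who do not meet limb 1.

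- If section 12 also means any time, S − O = a, which is zero or positive. O can be too low, never too high.
- If section 12 means scores present together, S − O = a − b, which can have either sign. For example, a subject with grade 4 erythema at one visit and grade 3 crusting only at a later one is in O but would not meet limb 2.

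The three single-score criteria are unaffected by this choice.

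**5. Size per subject.** Protocol 11.2 derives the safety set from the full analysis set, which leaves out the first two of 40 randomised subjects: 40 − 2 = 38. One subject is 1/38 = 2.6 percentage points, or 1/40 = 2.5 points if all randomised subjects are the denominator. The documents give no basis for estimating a or b.

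**The case against.** The strongest reply is that the SAP listing is not wrong for what it is called. It is labelled as LSR events, it uses the right LSR grades, and nothing in the SAP says it is the whole analysis of the 5.2 endpoint. That stands. The defect is that nothing else in the available text supplies the missing part.

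Second, 11.3.10 already points to section 12. It does, but generally, and the count written beneath that reference lists grades only.

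Third, the material for limb 1 may be visible elsewhere. All adverse events are listed, as are those leading to withdrawal or discontinuation; the reason for no treatment is shown; and SAP 6 lists all data. This limits the harm, but a listing without the judgement marked does not summarise the endpoint.

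Fourth, a summary may sit in the table shells, which SAP 6 places in a separate document. That cannot be excluded.

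Two stronger readings are tempting. A reader might infer that the cohort decisions were taken on a faulty stopping count. The documents do not support that. Section 12 says "Due to the design of the trial, there are no statistical criteria for trial termination", and the committee's material includes the adverse event list and a "List of individual component LSRs", so it can see more than the count. The SAP, effective 19 May 2017, also postdates the planned completion of the last subject in Q4 2016, so its listing could not have shaped reviews held on the planned timetable. A reader might also infer that the plan must under-report the endpoint. Step 4 shows that this follows only if section 12 is read as allowing scores from different times.

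**Conclusion.** The point holds as a minor inconsistency. The 5.2 endpoint and the section 12 frequencies use a two-limb definition; the 11.3.10 count and the SAP 4.4.1 listing that follows it use the LSR-grade limb alone; and no output in the available text counts the full endpoint. The passages must be reconciled.

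The size is unknown. The number of subjects meeting only limb 1 may be zero, and the net direction against section 12 depends on a timing rule that section 12 does not state. The endpoint is descriptive, and no hypothesis test depends on it.

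The conclusion assumes that the unseen material (table shells, committee charter, and the SAP text before 4.1) contains no such summary. If the shells do, only the cross-reference and the timing rule remain to be settled.

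**What to change.** Have SAP 4.4.1 cite the section 12 definition in place of 11.3.10, and align 11.3.10 as well if any cohort review is still to come. On the planned dates that second change is probably moot. State whether the scores in the two-or-more list must be present together or may occur at any time.

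Add one final table with the number and percentage of subjects meeting limb 2, limb 1 and either, with the denominator stated. Count limb 1 only where a recorded entry, such as the reason not to treat or the reason for withdrawal, shows that the investigator judged the event unacceptable. Classify those entries before the code is broken, where that is still possible.

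The cost is a change of SAP wording, one table, and the work of reading and classifying recorded reasons. The eCRF was not seen, so it is not known whether the recorded reason separates the investigator's judgement from the other criteria in 6.1. Limb 1 may be only partly identifiable, especially after Day 3. It should be labelled an incomplete proxy, so that the table does not look more definitive than its source. If limb 1 cannot be identified at all, report limb 2 alone and say that the 5.2 endpoint is only partly reported.

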4.4.2 Other safety endpoints

Vital signs will be presented as described in the protocol.

5 Programming and Quality Control

SDTM data sets are received from the data management provider Novella (formerly TKL). Larix will review the SDTMs and inform Novella and Leo of any deficiencies and discrepancies.

Larix will prepare ADaM data sets, ADRG and define file. ADaM data sets will be QCed by double programming.

Tables, listings and figures will be independently code reviewed by a qualified programmer (statistician for analysis programs) according to Larix SOPs.

ADaM data sets, tables, listings and figures will be produced by SAS ver. 9.4 following Larix' SOPs on programming.

6 Tables, Listings and Figures

The table shells are presented in a separate document.

The following figures will be prepared:

1. Mean and individual lesion count profiles
2. Plots of mean and individual profiles of composite LSRs by visit and lateral side
3. Plots of mean and individual profiles of maximum of right and left side composite LSRs by visit

All data will be listed by subject, visit and treatment (if relevant).

7 Change Log

| Edition | Effective on | Reason for revision |
|---------|--------------|---------------------|
| 1.0 | 19MAY2017 | New version |

Signature Page for TMF-000020290 v1.0

| | |
|------------------------------|--|
| Reason for signing: Approved | Management / Lead Approver Verdict(s) Name: PPD Capacity: Biostatistics Date of signature: 31-Aug-2017 07:36:20 GMT+0000 |
|------------------------------|--|

| | |
|------------------------------|--|
| Reason for signing: Approved | Approver Verdict(s) Name: PPD Capacity: Quality Control Date of signature: 31-Aug-2017 08:22:26 GMT+0000 |
|------------------------------|--|

Signature Page for TMF-000020290 v1.0
